7.2 Postoperative Outcomes

- Surgical outcomes: CRP level, SAA level, Drainage volume, intraoperative blood loss, VAS pain score, Operative time.
- Clinicopathologic characteristics: tumor size, number of lymph nodes, the positive rate of lymph nodes.
- Complications: complication rates and types.

7.3 Primary Outcome Measure: CRP level

8. Code of Ethics

8.1 Informed consent

Before each patient was enrolled in this study, the research investigators are responsible for a complete and comprehensive introduction to the surgical method of this study, its possible side effects and possible risks, and let patients know their rights, risks and benefits to be assumed. Patients should have signed informed consent before enrollment.

8.2 Ethical norms and policies and regulations

This clinical trial must comply with the Declaration of Helsinki (2000 Edition), the Good Clinical Practice (GCP) promulgated by the SFDA, and related regulations. Before the start of the trial, the study could be started only after the protocol was approved by the ethics committee of the lead unit. Any modification of the trial protocol during clinical research should be reported to the ethics committee and filed.

8.3 Obtaining ethics approval

Ethical approval has been obtained.

9. Quality Assurance

In order to ensure that this trial can be carried out in strict accordance with the clinical research protocol, during the entire process of the clinical trial, clinical investigators and clinical sponsors should behave in strict accordance with the requirements of the Good Clinical Practice for Drugs (GCP), and be sure to follow the trial procedures. Standardized, accurate test data, and reliable research conclusions. Specific requirements are as follows:

1. Requirements for collaborators:

- Lectures on clinical programs, CRF filling, etc. are given to the researchers before the clinical start.
- Send clinical monitors to conduct on-site inspections.
- Ensure that the researchers can keep in touch with the researchers at any time by telephone or email.

2. Requirements for researchers:

- Responsible for obtaining the "Informed Consent" signed by each subject or his agent.
- Complete the case report form (CRF) carefully as required.
- Regular visits.
- Completely maintain records of clinical records, and original medical records of subjects.

10. Data Processing and Preservation

10.1 Case report form (CRF)

The case report form should be filled out by investigators, and the CRF form should be filled out in time to ensure accurate content and timely summary. Generally, the CRF form should not be altered. If there is an error that needs to be revised, it should be signed at the revised place. The CRF form is in triplicate, and after the trial is over, it will be handed over to the clinical team leader hospital, the sponsor and the trial hospital for preservation. Data entry was performed after the completed case report was reviewed by the clinical monitor. The contents of the case report form are no longer modified.

10.2 Create a database

After receiving the CRF form, the statistician will verify the question by the researcher, and the researcher should answer and return as soon as possible. Statisticians will establish a database at the same time. After the database is reviewed, the data will be locked by the principal investigators, sponsors, statistician and clinical monitors. To ensure data security, irrelevant personnel cannot access and modify the data, and the data must be backed up.

10.3 Storage of data

The researcher should keep the data intact. According to the principle of GCP in China, for the investigators or hospitals, the data storage should be more than 5 years.

11. Statistical analysis

Professional statisticians undertake statistical analysis tasks and participate in the whole process from experimental design, implementation to analysis and summary. After the study protocol and case report form are completed, a statistical analysis plan shall be formulated. After some necessary modifications shall be made during the study process as required, and a statistical analysis report shall be provided after the data analysis is completed.

All analyses were performed using SPSS 26.0, and a P value less than 0.05 was considered significant. Normally distributed quantitative data are represented by mean (SD) [range]. Non-normally distributed quantitative data are represented by M (QR) . Comparison between groups was performed using the Mann-Whitney U test. Categorical data are expressed as frequencies and percentages. Comparisons between groups were performed using the χ^2 test or Fisher's exact test.

References:

2. Choi JY, Lee KE, Chung KW, et al. Endoscopic thyroidectomy via bilateral axillo-breast

- approach (BABA): review of 512 cases in a single institute. *Surg Endosc.* 2012;26(4):948-955.
 5. Sephton BM. Extracervical Approaches to Thyroid Surgery: Evolution and Review. *Minim Invasive Surg.* 2019;2019:5961690.

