**Single-center, Retrospective Study
of Retro - Auricular Single - Site
Endoscopic, Transoral Endoscopic
Thyroidectomy Vestibular Approach
and Transareola Endoscopic
Thyroidectomy in Patients With
Early Stage Papillary Thyroid
Carcinoma**

Study Protocol

Version date: February 11, 2023

Official Title	Single-center, Retrospective Study of Retro - Auricular Single - Site Endoscopic, Transoral Endoscopic Thyroidectomy Vestibular Approach and Transareola Endoscopic Thyroidectomy in Patients With Early Stage Papillary Thyroid Carcinoma
Brief Summary	The goal of this retrospective study is to compare the safety and efficiency of endoscopic thyroidectomy via retro - auricular single - site approach, transoral endoscopic thyroidectomy vestibular approach and transareola approach.
Conditions	Age: 18 ~ 70 years. Patients with early stage papillary thyroid carcinoma.
Sample Size	160
Inclusion Criteria	
 ● Age 18-70 years old, no gender restrictions. ● Fine-needle aspiration cytology(FNA) confirmed papillary thyroid carcinoma(PTC). ● Early stage PTC (stage T1N0M0). ● Preoperative ultrasonography showed unilateral glandular lobe malignant tumor and the largest diameter was not more than 2cm, without cervical lymph node metastasis and extensive metastasis. ● Patients undergoing thyroid lobectomy and central lymph node dissection. ● Patients who have signed an approved Informed Consent.
Exclusion Criteria	
 ● Patients who do not accept case data collection for various reasons. ● The clinical data unfit this study (at the discretion of the investigator) . ● Patients who have undergone neck surgery or radiotherapy before this trail. ● Patients who have uncontrolled hyperthyroidism.
Elimination Criteria	
 ● Patients who violated the requirements of the research protocol. ● The quality of data records is incomplete and inaccurate. ● Lost cases.
Study Completion	2023-02-28
Locations	1

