Thyroid cancer is one of the most common malignant tumors in the head and neck. Among it, papillary thyroid carcinoma accounts for about 70% of thyroid cancer. The degree of malignancy is low, but there is a tendency for multicentricity, and cervical lymph node metastasis occurs early. Due to the development of diagnosis technology, the amount of papillary microcarcinoma is getting higher and higher. At the same time, the change of aesthetic makes young women pursue a scarless neck^{1, 2}. Surgery is the first choice of treatments for early-stage thyroid cancer.^{3, 4} Traditional open surgery tended to leave a long scar on the neck, which affects the cosmetic outcome. At present, many reported approaches, such as trans-areola approach⁵, trans-axillary approach⁶, trans-oral approach^{7, 8} or some combined approaches⁹, all have wider flap dissection or greater body trauma, and at the same time, these above approaches are difficult to achieve complete dissection of central lymph nodes¹⁰. Therefore, based on the experience of transauricular hairline endoscopic thyroidectomy¹¹⁻¹³, we established a new operative method-the Retro-auricular single-site endoscopic thyroidectomy (RASSET). The incision is only 3cm and located at the posterior sulcus of the auricle, which can meet the cosmetic needs. Compared with other endoscopic approaches, the dissection area is small and the flap dissection is small, which may reduce the surgical trauma. The RASSET is easy to resect the upper pole of the thyroid gland, and can achieve complete dissection of the central lymph nodes. The article titled "A comparative study between retro - auricular single - site endoscopic thyroidectomy and transoral endoscopic thyroidectomy vestibular approach: a single - center retrospective analysis" has been published in "Chin J Surg"¹⁴. Guangdong Medical Information Research Institute recognized that there was no report of endoscopic thyroid surgery for this approach at home and abroad, and it also passed the new technology evaluation in the Sun Yat-sen University Cancer Center, and was recognized as an international leader.

Figure 1. A:Sun Yat-sen University Cancer Center Certificates(international innovation). **B:**Guangdong Medical Information Research Institute Certificates(no report of this approach). **C:**Zhonghua Wai Ke Za Zhi(a new approach).

2. Study purpose

2.1 Primary purpose:

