Compare the traumatic differences between the three groups by comparing the preoperative and postoperative CRP levels of the three groups.

2.2 Secondary purpose:

Compare the degree of surgical trauma between the three groups by comparing the level of SAA, blood loss, VAS pain score, and postoperative drainage.

Compare the clinicopathologic characteristics between the three groups by comparing the number of resected lymph nodes, and the positive rate of lymph nodes.

Compare the safety between the three groups by comparing the types and rate of complications.

2.3 Primary Outcome Measure:

CRP level

2.4 Secondary Outcome Measures:

- Cosmetic outcome: postoperative cosmetic outcomes
- Surgical outcomes: SAA level, blood loss, VAS pain score, postoperative drainage volume, Operative time.
- Clinicopathologic characteristics: tumor size, number of lymph nodes, the positive rate of lymph nodes.
- Complication: complication rates and types.

3. Study Eligibility

3.1 Inclusion Criteria:

- Age 18-70 years old, no gender restrictions;
- Patient must be suitable candidates for surgery;
- Be able to understand the purpose of the test;
- Preoperative ultrasound showed unilateral glandular lobe malignant tumor and the largest diameter was not more than 2cm, and preoperative imaging examination showed that the largest diameter of central lymph node was not more than 2cm without lateral cervical lymph node metastasis and extensive metastasis;
- Patients who have cosmetic requirements;
- Patients who have signed an approved Informed Consent

3.2 Exclusion Criteria:

- Patients who do not accept case data collection for various reasons.
- The clinical data unfit this study (at the discretion of the investigator) .
- Patients who have undergone neck surgery or radiotherapy before this trail.
- Patients who have uncontrolled hyperthyroidism.

3.3 Withdrawal criteria:

(A withdrawal case refers to a patient who withdraws from treatment for various reasons in study. Patients with the following conditions will be withdrawn from investigational treatment.)

- The patient himself or his legal representative requests to withdraw;
- In the opinion of the investigator, the patient's continued participation in the study will

be detrimental to his health.

3.4 Elimination Criteria:

- Patients who violated the requirements of the research protocol;
- The quality of data records is incomplete and inaccurate.
- Lost cases.

4. Case Screening

4.1 examination items

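### CRP is to be compared across three groups, but the only quantitative test named is the two-sample Mann-Whitney U at an unadjusted 0.05, with no pairs, three-group test or multiplicity rule stated

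*Combined protocol and SAP*

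**What the plan says.** Section 2.1 gives the primary purpose: "Compare the traumatic differences between the three groups by comparing the preoperative and postoperative CRP levels of the three groups". Sections 2.3 and 7.3 name CRP level as the primary outcome, without a time point or a summary such as change from baseline. Section 2.2 sets a parallel three-group aim: "Compare the degree of surgical trauma between the three groups by comparing the level of SAA, blood loss, VAS pain score, and postoperative drainage".

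Section 11 states the analysis. The threshold is "All analyses were performed using SPSS 26.0, and a P value less than 0.05 was considered significant". Normal data are to be summarised by mean and SD and non-normal data by M (QR). Then comes the only test for quantitative data: "Comparison between groups was performed using the Mann-Whitney U test". The χ² and Fisher tests that follow are for categorical data. Nothing names a three-group test for CRP, a reference group, a list of pairs or a multiplicity rule.

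Section 11 also says "After the study protocol and case report form are completed, a statistical analysis plan shall be formulated". The synopsis row headed Statistical Analysis Plan, however, repeats the same analysis text and adds nothing.

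**The concern.** The Mann-Whitney U test compares two samples. It cannot by itself answer a three-group question, so the analyst has to choose pairs. Three choices fit the text: all three pairs, RASSET (described in the Background as the authors' new method) against each of the other two, or a single pair. Each gives a different false-positive rate for the primary claim, and the plan does not choose.

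If all pairs are tested and any P<0.05 is reported as a difference in surgical trauma, a chance finding occurs about 2.4 times as often as 0.05 suggests (12.2/5). For the RASSET pairs only, the factor is 1.6 to 1.9 (8.0/5 to 9.6/5). The timing adds to this: the title block reads "Version date: February 11, 2023", 17 days before the stated completion date of 2023-02-28, in a retrospective study. A rule left open that late could be settled after results are known.

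**Working it through.** **Inputs from the documents.** Three groups (Section 2.1); threshold 0.05 per test, no adjustment (Section 11); total of 160 patients (synopsis). The plan states no familywise error or power, and the 160 cannot be re-derived because no effect size, SD, power or allocation is given.

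**Assumptions.** Two-sided tests; CRP tested as one variable; identical CRP distributions in all groups under the null. The readable text gives no group split (the flowchart is not shown), so five splits of 160 were tried, RASSET first: 53/53/54, 80/40/40, 100/40/20, 40/60/60, 20/70/70.

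**Step 1: normal-theory values, equal groups.**
- One pair: 5.0%.
- Two pairs sharing RASSET: 1 − P(|Z₁|<1.96, |Z₂|<1.96) with correlation 0.5 = 9.1%.
- All three pairs: P(studentized range for 3 groups, infinite df > 1.96 × √2 = 2.77) = 12.2%.

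Treating the three tests as independent gives 1 − 0.95³ = 14.3%, and the Bonferroni bound is 3 × 0.05 = 15%. Both overstate the error, because the pairs share groups.

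**Step 2: simulated Mann-Whitney tests** (100,000 null data sets per split; Monte Carlo standard error about 0.1 point).

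| Rule | Chance of at least one P<0.05 over the five splits |
|---|---|
| All three pairs | 11.8-12.2% |
| RASSET against each comparator | 8.0-9.6% |
| One pair named in advance | 4.9-5.1% |
| All pairs, only if Kruskal-Wallis P<0.05 | 4.9-5.1% |
| RASSET pairs, only if Kruskal-Wallis P<0.05 | 3.5-4.6% |

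Heavily tied data change little (all pairs 11.8-12.2%, gated 4.8-5.1%). If one group truly differs by 0.3-0.7 SD, the remaining null pair is falsely declared 3.3-5.1% of the time under the gate, so the gate also holds when only some groups differ.

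**Step 3: more than one CRP variable.** Section 2.1 mentions preoperative and postoperative levels. If both are tested over all pairs and are uncorrelated, the chance is 1 − (1 − 0.122)² = 22.9%. Simulation with equal groups and an assumed correlation of 0 to 0.6 gives about 21-23%. Gating each variable separately gives about 9-10% (uncorrelated: 1 − 0.95² = 9.75%). The gate therefore protects the primary claim at 5% only once a single CRP variable is fixed.

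**Step 4: power cost of the gate.** Assumed normal data, RASSET shifted 0.55 SD, RASSET versus the second group (standard error about 0.25 point):

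| Split | Ungated | Gated |
|---|---|---|
| 53/53/54 | 78% | 74% |
| 80/40/40 | 78% | 75% |
| 100/40/20 | 81% | 77% |
| 40/60/60 | 74% | 68% |
| 20/70/70 | 55% | 44% |

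With equal groups and other assumed shifts: 93% to 92% (0.7 SD), 51% to 43% (0.4 SD), 32% to 24% (0.3 SD). Bonferroni over three pairs at 0.55 SD would leave 63% (equal groups) and 37% (20/70/70).

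**The case against.** **The promised analysis plan could fill the gap.** Section 11 foresees a later plan. But the synopsis row with that title already carries the same text, so this defence is weak.

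**There may be no inflation.** The nominal range starts at 5%, and no stated rule makes any single P<0.05 a success. This stands in part: one pair fixed in advance would keep 5%. But the plan names no such pair, and one pair would not deliver the three-group comparison in Section 2.1.

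**The sentence may cover only non-normal data.** It directly follows the description of non-normal summaries. That reading is open, so one cannot say flatly that Mann-Whitney governs SAA, blood loss, VAS pain and drainage. On that reading, no test at all is named for normally distributed data. Either way CRP has no three-group test.

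**Stronger inferences the documents do not support.** A reader might take 12% as the study's false-positive rate, or as its maximum. It is neither: it depends on an unstated choice of pairs and on CRP being one variable. The 21-23% is conditional too, since preoperative CRP may be meant only as a baseline descriptor or covariate. A reader might also infer from the dates and the past tense of Section 11 that pairs were picked after the results were seen. The documents do not show that.

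**Kruskal-Wallis is not the only remedy.** This stands. If the aim is RASSET against each comparator, Holm over those two pairs is a fair rival. With RASSET shifted 0.55 SD from both, Holm is 1, 2 and 4 points more powerful at 53/53/54, 40/60/60 and 20/70/70, and 1 point less at 80/40/40 and 100/40/20. If RASSET differs from only one comparator (equal groups), the gate does better, 73% against 68%. Neither dominates.

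**Conclusion.** The point holds. The named test cannot make the comparison set as the primary purpose, and the missing choice of pairs leaves the nominal error of the primary claim undetermined: about 12% for all pairs, 8-10% for RASSET against each comparator, 5% for one pre-named pair. These figures assume a single CRP variable, two-sided tests, no true difference and an assumed split of 160; they vary little over the splits tried. If both CRP time points are tested over all pairs, the figure is about 21-23%.

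The rates are nominal. They take CRP distributions to be identical when the approaches have no effect, which a retrospective comparison ("The goal of this retrospective study is to compare the safety and efficiency of endoscopic thyroidectomy") without randomisation need not satisfy. Confounding is a separate problem, and not a reason to leave the primary test unspecified. Because this concerns the primary analysis and can be corrected without new data, it should be corrected.

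**What to change.** In Section 11 and the matching synopsis row:

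1. Define one primary CRP variable, for example postoperative CRP at a stated time, or the change from preoperative CRP.
2. Replace the Mann-Whitney sentence with: *The primary CRP variable and each other quantitative outcome analysed by ranks are compared across the three groups with the Kruskal-Wallis test at 0.05; pairwise Mann-Whitney U tests are interpreted only if the global P<0.05.*
3. If only RASSET against each comparator is intended, name those two pairs and apply Holm instead.
4. Say which test applies to any quantitative outcome treated as normally distributed.

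Date the change before any CRP result by group is seen. If results have been seen, say so and report the global P with every pairwise P.

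The cost is a few sentences in two places and no new data. Pairwise power falls as tabulated above: modestly with equal groups, more when one group is small or the true difference is small. The gate holds nominal error at about 5% for each variable tested, not across several variables, and does nothing about confounding.

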All cases must complete the following examination items before being considered for entry into this study. It is generally required to be completed within 7 days before treatment.

- Complete medical history and comprehensive physical examination, including symptoms, signs and specialist examination.
- Check items that must be done before routine treatment, including:

Blood routine: neutrophil/lymphocyte ratio,

Coagulation function: d-dimer,

Serological tests: CRP, SAA, procalcitonin, calcium level,

Thyroid function: TSH level, parathyroid hormone level,

Thyroid ultrasonography and FNA, thyroid Computed tomography scan if necessary,

Chest X-ray, abdominal ultrasonography, electrocardiogram.

The above examinations are all routine preoperative examinations, which do not cause additional financial burden on patients.

[figure not shown]

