4.2 Case screening

According to various examinations, those who meet the inclusion criterias are screened out.

The patients entered the study after completing the required examinations and being evaluated according to the inclusion criterias. Then sign the informed consent form and get treatment.

5. Study Process

Figure 2. flowchart

6. Surgical Technique

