7.1 Baseline Characteristics of Patients

Gender, Age, BMI, Tumor size, Pathological type, Tumor location, ASA grade.

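### Section 11 plans only unadjusted tests for a retrospective comparison of three approaches and leaves the role of preoperative CRP undefined, so measured case-mix differences could be read as differences in surgical trauma

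*Combined protocol and SAP*

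**What the plan says.** - **Tests.** Section 11, repeated in the Statistical Analysis Plan row of the summary table, says: "Comparison between groups was performed using the Mann-Whitney U test". Categorical outcomes get χ² or Fisher's exact tests, with significance at P below 0.05. No regression, matching, stratification, propensity method or covariate list appears. Section 11 also says that "a statistical analysis plan shall be formulated" once the protocol and case report form are complete.
- **Primary purpose.** Section 2.1: "Compare the traumatic differences between the three groups by comparing the preoperative and postoperative CRP levels of the three groups". Sections 2.3 and 7.3 name the outcome only as CRP level, with no time point and no statement of whether it is a postoperative value, a change or a baseline-adjusted value.
- **Data collected.** Section 4.1 lists among the preoperative tests "Serological tests: CRP, SAA, procalcitonin, calcium level". Section 7.1 lists the baseline characteristics: "Gender, Age, BMI, Tumor size, Pathological type, Tumor location, ASA grade". Neither list is given a role in the analysis.
- **Allocation.** The summary table calls the study retrospective. The available text describes no randomisation, matching or rule for choosing the approach. Section 5 consists of "Figure 2. flowchart", which is not reproduced in the text available for review.
- **Eligibility.** The summary table requires T1N0M0 disease, PTC confirmed by FNA, and lobectomy with central node dissection. Section 3.1 lists none of these and admits patients whose "preoperative imaging examination showed that the largest diameter of central lymph node was not more than 2cm".

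**The concern.** Section 2.1 treats a CRP difference as a difference in what the operation does to the patient. Without randomisation, an unadjusted test answers a different question: whether the patients who had each approach differ in CRP for any reason. If the groups differ in BMI, age, ASA grade or preoperative CRP, and that variable is related to postoperative CRP, the Mann-Whitney test attributes the result to the approach.

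The documents give one reason why groups could differ. Section 1 says that the retro-auricular route makes the upper pole easy to resect and that complete central dissection is difficult by the other routes. It does not say that surgeons chose the approach on that basis.

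The undefined preoperative CRP adds a second problem. The postoperative value, the change and a baseline-adjusted value are different analyses with different error rates when baselines differ, and the plan permits any of them.

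**Working it through.** **Inputs.** From the documents: total sample size 160, three groups, threshold 0.05. Not given, and therefore assumed: an equal split (160/3, so 53 per group), two-sided tests, outcomes in SD units, and every imbalance and correlation below. The 160 has no stated power, effect size, SD or group split, so it cannot be reproduced.

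**1. Bias from one measured covariate.** Bias = imbalance (SD) × correlation with postoperative CRP. Imbalance 0.3–0.5 and correlation 0.2–0.5 give 0.3 × 0.2 = 0.06 SD up to 0.5 × 0.5 = 0.25 SD.

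**2. False-positive rate of one unadjusted Mann-Whitney test, no true effect.** With efficiency 3/π, λ = bias × √((3/π) × 53/2) = bias × 5.03, and the rate is Φ(λ − 1.96) + Φ(−λ − 1.96).

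| Bias (SD) | λ | 53 v 53 | 80 v 40 | 40 v 40 |
|---|---|---|---|---|
| 0 | 0 | 5.0% | 5.0% | 5.0% |
| 0.06 | 0.30 | about 6% | 6.1% | 5.8% |
| 0.10 | 0.50 | 7.9% | 8.0% | 7.2% |
| 0.15 | 0.75 | 11.7% | 11.8% | 10.0% |
| 0.25 | 1.26 | 24.2% | 24.3% | 19.4% |

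With no imbalance or no correlation the rate stays at 5%.

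**3. Why the definition of CRP matters.** Simulation, 53 per group, preoperative CRP differing by 0.5 SD, no true effect:

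| Pre/post correlation | Mann-Whitney, postoperative | Mann-Whitney, change | Baseline as covariate |
|---|---|---|---|
| 0.3 | 11% | 32% | 5% |
| 0.7 | 41% | 15% | 5% |

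Neither unadjusted choice is safe, and which one is worse depends on a correlation that the documents do not give.

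**4. Limits of adjustment.** With a measured bias of 0.25 SD plus an unmeasured 0.10 SD in the same direction, simulation gives about 41% unadjusted and 9% adjusted. With opposing biases (+0.15 measured, −0.10 unmeasured) it gives about 6% unadjusted and 8%–9% adjusted. Adjustment returns the rate to 5% only if the modelled covariates carry all the confounding.

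**5. Calendar time.** Suppose date of surgery explains a share R² of the contrast between two approaches. The date imbalance is then 2√(R²/(1 − R²)): 2.0 SD at R² 0.50 and 3.46 SD at 0.75. If date correlates 0.05–0.10 with CRP, a linear model without date rejects 8.1%–17.7% of the time (R² 0.50) or 14.5%–43.0% (R² 0.75). Adding date widens the 95% CI half-width from 1.96 × √(2/53) = 0.38 SD to 0.38/√(1 − 0.50) = 0.54 SD or 0.38/√(1 − 0.75) = 0.76 SD.

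**6. Room for the model.** Seven covariates take roughly 7 to 10 degrees of freedom, depending on the categories of location and ASA grade. Residual df are 160 − 3 − (7 to 10) = 147 to 150 with complete data. Section 3.4 eliminates cases where "The quality of data records is incomplete and inaccurate"; if 20% were lost, 128 patients would leave 115 to 118.

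**The case against.** - **No imbalance is shown.** This is correct. A reader might infer that the groups do differ, or that surgeons selected patients by anatomy. The documents contain no group characteristics and do not say so. Every rate above follows from assumed inputs, and at the low end 6% against 5% is negligible.
- **Preoperative CRP is not really undefined.** Section 2.1 can be read as comparing the groups on the preoperative level and again on the postoperative level with the same test. The baseline variables could be compared too, so imbalance would be visible. That is a fair reading, but seeing an imbalance does not remove it from the primary result, and a non-significant baseline test does not show balance.
- **Eligibility makes the groups comparable.** It does so only in part, and the two eligibility lists disagree on stage, cytology and extent of surgery. Requiring disease in one lobe does not restrict left or right. Neither list restricts sex, BMI, tumour location or ASA grade, and both allow ages 18–70.
- **A later SAP may deal with it.** Section 11 promises one, but the only text labelled as such repeats the unadjusted tests.
- **The flowchart may explain the grouping.** It may. A grouping rule would still not define how preoperative CRP is used or supply an adjusted analysis.

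**Conclusion.** The point holds as a risk built into the plan, not as a demonstrated bias. Following section 11 as written leaves any measured confounding in the primary result, although the variables needed to reduce it are already collected. The size is unknown. The 6%–24% per-pair range rests on 53 per group, imbalances of 0.3–0.5 SD and correlations of 0.2–0.5, all assumed; other inputs would give other figures.

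A reader might go further and infer that an adjusted model would isolate the effect of the approach. The documents do not support that. Unmeasured factors and calendar time would remain, and the opposing-bias case shows that adjustment can even raise the error rate somewhat. This is an inexpensive improvement to the primary analysis.

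**What to change.** 1. **Primary analysis.** Compare postoperative CRP, at one stated time point, across the three approaches with adjustment for preoperative CRP, age, sex, BMI, tumour size on preoperative ultrasound, tumour location and ASA grade. A linear model of log CRP is one option; a rank-based or ordinal adjusted model suits heavily skewed or censored values. Use the preoperative ultrasound size because tumour size is listed both as a baseline variable (section 7.1) and as an outcome (sections 2.4 and 7.2).
2. **Order of testing.** Do an overall 2-df test of approach before the pairwise contrasts, and give 95% CIs for all contrasts.
3. **Other quantitative outcomes.** Apply the same adjustment where feasible, with preoperative SAA for SAA. Keep the planned tests as supportive and label them unadjusted.
4. **Calendar time.** Report the calendar range of each approach and a sensitivity analysis adding date of surgery, with both estimates and CIs side by side. Do not attach a rule that withholds the conclusion only if the direction changes. In the assumed date setting (correlation 0.10), such a rule would let through about 92% of false positives at R² 0.50 and 69% at R² 0.75, and it is not defined for three contrasts.
5. **Eligibility.** Reconcile the summary table with section 3.1.
6. **Reporting.** Describe results as associations with residual and calendar-time confounding.

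**Cost.** A little more analysis, a CRP time point to state, surgery dates to retrieve, and wider intervals in the date-adjusted analysis. The promised SAP can hold the model, but section 8.2 requires protocol changes to be reported to the ethics committee and filed. Only 17 days separate the version date (11 February 2023) from study completion (28 February 2023), so the model must be labelled post hoc if data have been examined.
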